5.2 Chemotherapy

Standard treatment for GIST with TKI-based therapy.

5.3 Duration of Therapy:

Patients can receive 2 doses of Injectafer® IV, given 7 days apart for a total of up to 1500 mg, or oral iron supplement e.g. Ferrosequels, BID, or ferrous sulphate, TID for 3 months, whichever arm they were assigned originally. If the patient on arm B does not tolerate oral preparations (even one dose of oral iron per day), then the patient can come off the protocol and receive IV iron as per standard of care.

6.0 Pretreatment Evaluation

- Standard History and Physical examination including weight and height and performance status (appendix D)
- Laboratory studies will include a CBC with differential, and platelet count, electrolytes and serum chemistries.
- Serum beta hCG or urinary pregnancy test (when indicated).
- All screening labs/pretreatment evaluations can be done within 1 week before registration.

7.0 Evaluation During Study

- Interim History and Physical examination including weight will be done before and after 3 months of the initiation of treatment.
- CBC differential and platelet counts will be monitored at least once a week for 3 months.
- Serum electrolytes and chemistries will be performed prior to and as frequently as needed during the treatment.
- Serum iron, serum ferritin, and total iron binding capacity (TIBC), and percentage serum transferrin saturation (TSAT) will be done at baseline, and every month for 3 months and then at 6 months.
- Patients will report the FACT-Fatigue and energy score at baseline and every month for 3 months and then at 6 months. In addition, patients will continue to report on daily symptom record diary the adverse events for 3 months [24].
- Management of hypersensitivity to the study drug: Patients with allergic reactions can be symptomatically managed. All patients with grade 4 hypersensitivity reactions (anaphylaxis) will be removed from the study.

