2.4.2 Clinical Experience

The efficacy of Injectafer® for the treatment of IDA was demonstrated in 2 randomized, open-label, controlled clinical studies (1VIT09030 and 1 VIT09031). In these 2 studies, Injectafer® was administered at a dose of 15 mg/kg body weight up to a maximum single dose of 750 mg of iron on 2 occasions separated by at least 7 days up to a cumulative dose of 1500 mg of iron [21-23].

Study 1 VIT09031 enrolled subjects with iron-deficiency anemia who had an unsatisfactory response to oral iron or who were intolerant to or inappropriate for oral iron therapy during the 14-day, oral iron run-in period. Study 1VIT09030 enrolled subjects with iron-deficiency anemia and impaired renal function [21-23].

The overall incidence of treatment-emergent serious adverse events in the 2 studies was 12.8% in the Injectafer® group and 12.5% in the pooled comparators group. No notable differences (1.0% and at least a 2-fold difference in incidence) were observed between the Injectafer® group and the pooled comparators groups for specific events.

The overall incidence of treatment-emergent adverse events resulting in premature discontinuation of study drug was 2.9% in the Injectafer® group and 2.1% in the pooled comparators group. The most common treatment-emergent adverse events resulting in premature discontinuation of study drug in the Injectafer® group were flushing and hypertension (0.5% and 0.6%, respectively) [21-23].

The percentage of subjects with treatment-emergent low phosphorus, defined as a baseline value that was Grade 0, 1, or 2 and decreased to a value defined as Grade 3 (<2.0 to 1.0 mg/dL) or Grade 4 (<1.0 mg/dL) per Common Terminology Criteria for Adverse Event version 3.0, was the only notable difference between the Injectafer® (29.6%) and the pooled comparators (0.7) groups. Mean decreases from baseline in phosphorus in the Injectafer® group were highest at Day 14 and were returning toward baseline at Day 28/35 in Studies 1VIT09030 and 1VIT09031. The trend toward baseline continued through Day 56 in Study 1VIT09030 [21-23].

Safety results for 5799 Injectafer®-treated subjects treated in 20 short-term Phase 2/3 studies of iron-deficiency anemia or congestive heart failure (CHF) were similar to studies 1VIT09030 and 1VIT09031 [21-23].

In summary, Injectafer® is a safe and effective treatment of IDA in adult patients who are [20]:

- Intolerance to oral iron or have had unsatisfactory response to oral iron;

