8.0 End of Study/Early Withdrawal

Standard History and Physical examination including weight will be documented. Laboratory studies will include a CBC with differential, and platelet count.

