9.0 Criteria for Response

9.1 Response

All patients who receive one dose of study drugs under this protocol will be evaluable for toxicity. All patients randomized will be considered evaluable for response in the intent-to-treat analysis.

Efficacy assessments will include:

- Hemoglobin, TSAT, and other iron panel test measures
- Patient reported outcomes questionnaires (FACT-Fatigue)
- The use (or lack of use) of other therapies for anemia (eg, RBC or whole blood transfusions, ESA, or both)

9.2 Response will be defined as proportion of achieving an increase in hemoglobin at any time from baseline to end of 3 months, as described below:

Complete response (CR): increase in HGB ≥ 2.0 g/dL above baseline, and/ or
transfusion free.

Partial response (PR): increase in HGB (≥ 1 g/dL- 2 g/dL) above baseline

Minor response (MR): increase in HGB (≥ 0.5 g/dL- 1 g/dL) above baseline

9.3 Toxicity: Toxicities will be graded using the Common Terminology Criteria for Adverse Events v4.03 – CTCAE (see Appendix C). Uncomplicated, severe, or life threatening neutropenia and thrombocytopenia are expected toxicities of the systemic therapy and as such will not be collected as adverse events in this study since the data is already captured through the CORe.

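### No chemistry draw is fixed after baseline, so the by-arm toxicity table may under-detect, or detect unequally, the low phosphorus that the protocol itself cites for Injectafer

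*Combined protocol and SAP*

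**What the plan says.** **Sampling.** Section 6.0 sets the pretreatment tests: "Laboratory studies will include a CBC with differential, and platelet count, electrolytes and serum chemistries". It lists no individual analytes. For the study period, section 7.0 says "Serum electrolytes and chemistries will be performed prior to and as frequently as needed during the treatment". For end of study or early withdrawal, section 8.0 says "Laboratory studies will include a CBC with differential, and platelet count" and adds no chemistry. None of the three sections names phosphorus. By contrast, section 7.0 fixes the CBC at weekly intervals for three months, and the iron panel at baseline, monthly for three months and at month 6.

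**The known signal.** Section 2.4.2 says that treatment-emergent low phosphorus "was the only notable difference between the Injectafer® (29.6%) and the pooled comparators (0.7) groups". The event is "defined as a baseline value that was Grade 0, 1, or 2 and decreased to a value defined as Grade 3" (below 2.0 down to 1.0 mg/dL) or Grade 4 (below 1.0 mg/dL), graded "per Common Terminology Criteria for Adverse Event version 3.0". On timing: "Mean decreases from baseline in phosphorus in the Injectafer® group were highest at Day 14 and were returning toward baseline at Day 28/35". In the renal-impairment study the recovery continued to Day 56.

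**The analysis.** Toxicity is secondary objective 1 (section 1.0). Section 9.3 says "Toxicities will be graded using the Common Terminology Criteria for Adverse Events v4.03". Section 11.0 plans frequency tables overall and by arm, covering everyone who took one dose. It sets no test or threshold, and does not say how patients without a given laboratory result are shown. Section 5.1 makes the trial open label.

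**The concern.** The background section identifies one laboratory event that separates this drug from its comparators and says roughly when to look for it. The schedule then requires no measurement at that time, or at any time after baseline.

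A graded phosphorus value cannot come from the symptom diary or the physical examination. Section 13.1 requires adverse events found by laboratory assessment to be documented, but that reaches only tests that are done. A site could follow the plan exactly and record no such event.

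Two things are at stake in the toxicity table. Events may go unseen. And because staff know the assignment and decide when a test is needed, the two arms may be tested at different rates, so a by-arm comparison would partly reflect testing habits. A low count could not then be told apart from little testing.

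**Working it through.** **The plan's own figure.** The documents give no figure for detecting toxicity. The only power statement (section 11.0: 93% with 25 per arm, complete response 75% against 28.6%, two-sided 0.05) concerns the primary endpoint. A pooled-variance chi-square calculation gives 93.3%, so it is reproduced, and nothing below bears on it.

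**Does the schedule reach the cited times?** Arm A receives two doses 7 days apart (section 5.1). If Day 14 is counted from the first dose (an assumption), it falls about a week after the last Arm A dose. Adverse event collection is not the obstacle. The shorter stated window, 30 days after last study drug, ends in Arm A at 7 + 30 = day 37 (day 38 if the first dose is Day 1). The other window runs to study completion. Both cover Day 14 and Day 28/35. What is missing is a required draw.

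**Expected counts if the cited rates applied.** Inputs: 25 per arm (section 5.1); 29.6% and 0.7% (section 2.4.2).

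- Arm A: 25 × 0.296 = 7.4 events
- Arm B: 25 × 0.007 = 0.175 events, about 0.2
- True difference: 29.6 − 0.7 = 28.9 points

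**Effect of incomplete detection.** Let a and b be the shares of true events detected in Arms A and B. The documents give neither, so each may lie anywhere from 0 to 1. The observed difference in points is 29.6a − 0.7b.

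| a | b | Arm A events seen | Observed difference (points) |
|---|---|---|---|
| 1 | 1 | 7.4 | 28.9 |
| 0.5 | 0.5 | 3.7 | 14.45 |
| 0.25 | 1 | 1.85 | 6.7 |
| 0.25 | 0 | 1.85 | 7.4 |
| 1 | 0 | 7.4 | 29.6 |

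With equal detection below 100%, the part of missed events that falls in Arm A is 29.6 / (29.6 + 0.7) = 29.6 / 30.3, about 98%. On these rates, unequal testing could inflate the difference by at most 29.6 − 28.9 = 0.7 points.

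**How far this depends on the Arm B rate.** Suppose instead that the true Arm B rate were 5% or 10% (assumptions; the documents give no background rate for these patients). With a = 1 and b = 0, the observed difference stays at 29.6 points while the true one is 24.6 or 19.6. The inflation is then 5 or 10 points. The direction of the error is therefore conditional on the cited rates.

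**Why the number tested matters.** Suppose Arm A shows no events. The exact two-sided 95% upper limit for 0 of n is 1 − 0.025^(1/n): 13.7% for n = 25, 30.8% for n = 10, 52.2% for n = 5. The values 10 and 5 are illustrations. A zero over 25 treated patients means something quite different if only 5 of them were tested.

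**The case against.** The strongest reply is that this is a design preference. No passage contradicts another on chemistry timing. Low phosphorus is not a named endpoint; the objective is toxicity in general. The protocol presents it as an already characterised laboratory change that was recovering, and describes safety in 5799 treated subjects as similar. The toxicity table is descriptive, and a 50-patient phase II trial need not re-estimate a known effect. The size of any loss is also not shown: routine chemistry during TKI care could bring detection close to complete.

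Much of this stands. It limits the point to a cheap improvement and rules out any stated size of loss. It does not remove the gap, because the plan neither controls the detected share nor reports it.

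A reader might infer more than the documents support:

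- *That phosphorus will not be measured.* Section 6.0 lists no analytes, so local chemistry panels may include it.
- *That chemistry stops in Arm A after the second dose*, because section 7.0 speaks of the treatment period and Arm A dosing lasts a week. The wording leaves testing to need; it does not forbid a later draw.
- *That the table will necessarily favour Injectafer.* That needs the cited rates to hold. They come from two iron-deficiency anemia studies, one in impaired renal function, whereas this trial enrols GIST patients starting or receiving TKIs with creatinine below 1.5 mg/dL. Open-label staff might also test Arm A more often.
- *That a missed Day 14 draw loses the event.* Section 2.4.2 reports mean falls by day, not Grade 3/4 incidence by day. With recovery continuing to Day 56 in one study, later as-needed tests might still find low values. Equally, nothing shows that draws at weeks 2 and 4/5 would catch every case.

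**Conclusion.** The point holds in a limited form. No post-baseline chemistry is required and phosphorus is named in no study assessment, so the by-arm toxicity table may under-detect the one notable laboratory difference that the protocol cites, or detect it unequally by arm.

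If the cited rates carried over, the loss would fall mainly in Arm A, where about 7.4 of 25 events would be expected against 0.2 of 25 in Arm B. That rests on three assumptions: 0.7 is a percentage, the rates transfer to this population, and CTCAE v3.0 grading is comparable with the v4.03 used here. The detected share is unknown, so no actual loss can be stated. The consequence is confined to a descriptive secondary safety table; the complete response endpoint, its power and the sample size are untouched.

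**What to change.** In section 7.0, name serum phosphorus at the same fixed times in both arms:

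- baseline, because the definition in section 2.4.2 needs a baseline grade;
- week 2, with a weekly CBC draw;
- week 4/5, with the month-1 iron panel.

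In section 11.0, tabulate treatment-emergent Grade 3/4 low phosphorus by arm. State the grading thresholds used, since the cited rates and this trial use different CTCAE versions, and give the number tested as denominator.

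**Cost.** 50 patients × 3 draws = 150 scheduled assays, fewer in addition where local panels already include phosphorus. The blood draws are already required, with possibly one extra tube at week 2. Section 7.0 does not say where weekly CBCs are taken; if off site, the week-2 sample must be arranged. Section 13.1 requires abnormal laboratory values to be followed until they return to baseline or stabilise. On the cited rates that means repeat draws for about 7.4 + 0.175 = 7.6 Grade 3/4 cases, plus any lower-grade events.

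The change concerns measurement and reporting only. No treatment rule is proposed.

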Ferric Carboxymaltose (Injectafer®) will be provided by Luitpold Pharmaceuticals, Inc. from the commercial drug supply according to Good Manufacturing Practices (GMP).

It is the responsibility of the clinical investigator or trained designee to ensure that all study drug received at the site is inventoried and accounted for throughout the study by the designated personnel and is recorded in the inventory log kept with the pharmacy study documentation. The drug accountability will be verified by a trained designee upon completion of the study. Study drug will be stored in a secured area with restricted access to the dosing preparers only.

The clinical investigator or trained designee must store all study drugs pending reconciliation. The investigator agrees that study drug(s) will be dispensed by the investigator or sub-investigator(s) named on the Investigator Agreement or their qualified designees. The investigator, sub-investigators, or qualified designees also agree that the study drug(s) will be dispensed only to study subjects who have provided written informed consent and have met all entry criteria and in accordance with the instructions provided in the pharmacy manual.

After study drug reconciliation, the clinical site may destroy used/unused study drug product locally in accordance with all applicable institutional standard operating procedures, local and federal laws. Documentation of such destruction must be recorded and provided Luitpold Pharmaceuticals, Inc.

D. Contraindications

Hypersensitivity to Injectafer® or any of its inactive components.

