4.0 Patient Eligibility

Inclusion Criteria

- 1) GIST patients with IDA planned to start or receiving systemic therapy with TKIs
- 2) Evidence of iron deficiency anemia including, Hgb \leq 11 g/dL, but \geq 8 g/dL; and transferrin saturation (TSAT) $<$ 20%.
- 3) No H/O allergic reaction to iron therapy.
- 4) No clinical signs active of bleeding.
- 5) Adequate hematologic (ANC $>$ 1500/mm³, platelet count $>$ 100,000/mm³), renal (serum creatinine $<$ 1.5mg/dL), hepatic (serum bilirubin count $<$ 1.5 x normal and SGOT or SGPT $<$ 3 x normal) functions.
- 6) Patients must have Eastern Cooperative Oncology Group (ECOG) performance status of 0 – 2.
- 7) Signed informed consent to the study.
- 8) Male and Females of child bearing potential must use acceptable methods of birth control which include oral contraceptives, spermicide with either a condom, diaphragm or cervical cap, use of an intrauterine device (IUD) or abstinence.
- 9) Patients are required to read and understand English to comply with protocol requirements.
- 10) Age \geq 18 years old.
- 11) Life expectancy of at least 6 months.

Exclusion Criteria

- 1) Pregnant or lactating women.
- 2) Patients with any co-morbid condition which renders patients at high risk of treatment complication.
- 3) Patient has uncontrolled angina, congestive heart failure (New York Heart Association > class II or known ejection fraction $<$ 40%), uncontrolled cardiac arrhythmia or hypertension, or acute myocardial infarction within 3 months.

- 4) Patient has an active seizure disorder. (Patients with a previous history of seizure disorders will be eligible for the study, if they have had no evidence of seizure activity, and they have been free of antiseizure medication for the previous 5 years).
- 5) Psychological, social, familial, or geographical reasons that would prevent scheduled visits and follow-up.
- 6) Prior surgery or radiotherapy (RT) within 2 weeks of study entry.
- 7) Known hypersensitivity reaction to any component of ferric carboxymaltose.
- 8) Any anemia treatment within 4 weeks before inclusion (oral iron, IV iron, or erythropoiesis-stimulating agents), or transfusion of PRBCs in 2 weeks.
- 9) Hemochromatosis or other iron storage disorders.
- 10) Known positive hepatitis with evidence of active disease.
- 11) Patients with overt bleeding.
- 12) Ferritin \geq 800 ng/mL.

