5.0 Treatment Plan

5.1 Study Drug Treatment

This is an open label, randomized, phase II trial. Approximately 50 evaluable subjects will be randomly assigned to arm A and arm B (1:1).

Prior to randomization, all patients will be stratified into < 10g/dL vs. \geq 10g/dL.

Treatment Plan:

Fifty patients with GIST will be randomized 1:1 into two treatment arms; total 25 patients in each of the two arms:

Arm A/ investigational arm: all subjects (n=25) will receive 2 doses of Injectafer® at 15 mg/kg for a maximum single dose of 750 mg, given 7 days apart for a total of up to 1500 mg. The first IV infusion will be given prior to starting systemic therapy. The dose will be repeated 1 week later. It will be diluted in no more than 250 mL of normal saline and infused over 15 minutes.

Arm B/control arm: all patients (n=25) will receive oral iron (dose equivalent of 150-200 mg of elemental iron/day) supplement daily (such as Ferrosequels, BID, or ferrous sulphate, TID) for 3 months. Different iron preparation can be used based on patient's tolerance/preference.

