10.0 Criteria for Discontinuation from Treatment

Patients may be discontinued from study treatment at any time. Specific reasons for discontinuing treatment include the following:

- Serious or life-threatening adverse event
- Risk to patients as judged by the Investigator and/or Sponsor
- Severe noncompliance with protocol as defined by not receiving at least 70% of the planned treatment (judged by the Investigator and/or Sponsor).
- Request of the patient
- Patient becomes pregnant
- Progressive disease
- Investigator becomes aware of conditions or events that suggest a possible hazard to patients if the clinical study continues

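### Hypersensitivity is an ungraded contraindication in section 3.1.D, but sections 5.1, 7.0 and 10.0 as written still allow a second Arm A infusion after a reaction below grade 4 to the first

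*Combined protocol and SAP*

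**What the plan says.** Five parts of the combined protocol and SAP bear on a hypersensitivity reaction to the first infusion.

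- Section 3.1, part D (contraindications) has a single entry: "Hypersensitivity to Injectafer® or any of its inactive components". It names no grade.
- Section 5.1 gives every Arm A patient two doses, each up to 750 mg, seven days apart. Of the second it says "The dose will be repeated 1 week later". How the first dose was tolerated is not mentioned.
- Section 7.0 is the only place that deals with on-study hypersensitivity. It says "Patients with allergic reactions can be symptomatically managed" and then "All patients with grade 4 hypersensitivity reactions (anaphylaxis) will be removed from the study".
- Section 10.0 opens with "Patients may be discontinued from study treatment at any time". Its listed reasons include "Serious or life-threatening adverse event" and the investigator's or sponsor's own view that the patient is at risk. Hypersensitivity is not named.
- Section 10.1 keeps patients who stop treatment in follow-up unless one of four events occurs: withdrawn consent, loss to follow-up, death or study termination.

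Section 4.0 also screens on this history at entry, through inclusion criterion 3 ("No H/O allergic reaction to iron therapy") and exclusion criterion 7 ("Known hypersensitivity reaction to any component of ferric carboxymaltose"). Neither carries a grade.

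**The concern.** Whether to give the second infusion after a reaction to the first is the main safety decision for an individual Arm A patient. The protocol states a contraindication in its drug-information section. It then gives a dosing schedule and an on-study rule that neither repeat the contraindication nor refer to it. The one grade named in the on-study rule is grade 4. A reader who works from sections 5.1 and 7.0 could take that as the only threshold that matters and re-expose a patient whom section 3.1.D contraindicates. A reader who works from 3.1.D would withhold the dose. Two patients with the same reaction could then be handled differently, depending on which section the treating clinician consulted. Patient safety is at stake first. After that come the dose delivered in Arm A and the toxicity data for secondary objective 1.

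**Working it through.** The plan gives no figure to reproduce and no reaction rate, so the check is a comparison of the text. The inputs are sections 3.1.D, 4.0, 5.1, 5.3, 7.0, 10.0, 10.1 and 13.2. Three cases are traced through them.

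**Case 1: a non-serious reaction below grade 4 at infusion 1.**

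| Section | What it implies for infusion 2 |
|---|---|
| 3.1.D | Contraindicated, if ungraded wording covers all grades |
| 4.0 | Nothing; the criteria apply at entry |
| 5.1 | Due one week later, unconditionally |
| 5.3 | Permitted; it describes two doses as what patients can receive |
| 7.0 | Symptoms can be treated; no removal; silent on the next dose |
| 10.0 | May be withheld on judged risk; not required |
| 10.1 | If withheld, follow-up continues |

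Giving infusion 2 is consistent with 5.1, 5.3, 7.0 and 10.0 and inconsistent with 3.1.D. Withholding it is consistent with 3.1.D, 5.3, 7.0, 10.0 and 10.1, and departs from the 5.1 schedule only in a way that 10.0 permits. Section 3.1.D is thus the only text that would prevent the second dose, and neither 5.1, 7.0 nor 10.0 points to it.

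**Case 2: a reaction below grade 4 that is serious, for example because it leads to admission.** Section 13.2 classes an event as serious on outcome, not on grade, so this can occur. The serious-event reason in 10.0 then applies, but its opening sentence is still permissive. Section 7.0 does not forbid stopping. The two sections are compatible, and a second infusion is still not ruled out by either.

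**Case 3: a grade 4 reaction.** Section 7.0 removes the patient from the study, not merely from study drug. None of the four events in 10.1 that end follow-up is a hypersensitivity reaction. The two sections therefore disagree on whether follow-up continues, although 9.1 and 11.0 keep every randomized patient in the intent-to-treat efficacy analysis.

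**Size.** All 25 planned Arm A patients are scheduled for a second infusion, so 25 is the upper bound on those for whom the question could arise. Without a reaction rate in the documents, no expected number can be given.

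**The case against.** The strongest reply is that nothing here compels re-dosing. Section 7.0 governs removal from the study, and treating symptoms describes care of the reaction, not a decision on the next dose. Section 10.0 lets treatment stop at any time, including on judged risk, which reaches non-serious reactions of any grade. A clinician can withhold infusion 2, keep the patient in follow-up under 10.1 and remove only grade 4 cases, without breaching 3.1.D, 7.0, 10.0 or 10.1. This stands, and it rules out several stronger readings that a reader might infer:

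- That the protocol gives opposite instructions on the second dose. It does not: 7.0 is silent on that dose and 10.0 is discretionary.
- That 7.0 and 10.0 conflict after an admission. They do not, as Case 2 shows.
- That the entry criteria in 4.0 set a competing on-study threshold. They concern history before enrolment, and an entry criterion may differ from an on-study rule without contradiction.
- That withholding one of two doses breaches the 70% compliance limit in 10.0. That item concerns severe noncompliance as judged by the investigator or sponsor; a dose withheld for a reaction is not evidently that.
- That the analysis populations are damaged. Efficacy is by intention to treat and toxicity includes anyone given one dose, so neither set changes.

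The reply does not remove the gap. Discretion to stop is not a rule that prevents the second dose. The default in 5.1 is to give it, and the protocol does not say whether the specific on-study rule in 7.0 or the general contraindication in 3.1.D prevails.

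**Conclusion.** The concern holds in a limited form. The protocol states a contraindication without a grade limit, and its schedule and on-study rules, followed as written, allow a patient who meets that contraindication to receive the second infusion. This is a safety rule that the operative sections do not carry through; it is not a direct order to re-dose. The conclusion rests on one reading: that ungraded wording in 3.1.D covers reactions of every grade. The words themselves do not say so, but nothing in the section narrows them. The effect on the planned analyses is small, and the number of patients affected cannot be stated. The reason to act is patient safety and consistent handling, and the correction is cheap. Nothing here says which threshold is clinically right.

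**What to change.** The sponsor and investigator should reconcile sections 3.1.D, 5.1, 7.0, 10.0 and 10.1 into one consistent rule on whether the second infusion may follow a reaction to the first. They should choose the threshold themselves. The rule should sit in one place, with cross-references from the other sections. It should state separately what ends study drug and what ends study participation, so that follow-up under 10.1 continues for a patient who stops treatment. The decision on the second dose after any first-infusion reaction should be recorded. Section 13.1 already requires adverse events to be documented with intensity and attribution, so only that decision is new.

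The cost is a wording amendment and one case report form item. Depending on the threshold chosen, some Arm A patients may have their second dose handled differently from what 5.1 now implies.
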